## 1.0 Objectives

### 1.1 Study Objectives

This study will examine the neuro-pharmacological (pharmacokinetics and pharmacodynamics) profile of posaconazole (PCZ), in people with primary or recurrent high-grade gliomas (HGGs) requiring open surgical resection.

### 1.2 Primary Study Endpoints

Establish the neuro-pharmacokinetic profile of posaconazole, using microdialysis catheters (MDC). This will be based on the assessment of the concentration versus time curves of drug in the dialysate fluid, collected over a 24-hour period after surgery.

## 2.0 Background

### 2.1 Scientific Background and Gaps

#### High grade gliomas

High grade gliomas (HGGs, WHO Grade III and IV gliomas) are the most common malignant primary brain tumor in humans. Glioblastoma (GBM, WHO Grade IV glioma) is the most aggressive brain tumor, accounting for more than half of all gliomas and 17% of all primary brain and central nervous system (CNS) tumors[4]. Far from the importance of GBM being the most common human malignancy, GBM deserves attention on the basis of its universally poor prognosis.

Decades of research has demonstrated various degrees of molecular, genetic, epigenetic, and metabolic heterogeneity among tumors of the same grade and even within individual tumors [7]. This heterogeneity has significantly hampered efforts toward developing effective therapeutic strategies for GBM patients. From a metabolic perspective, it is well-known that most tumor cells preferentially convert glucose to lactate, regardless of the levels of available oxygen; this is known as aerobic glycolysis (or Warburg effect) [8, 9].

#### The Warburg effect and its role in HGGs

In HGGs, as with most cancers, cells have undergone effective reprogramming of their energy metabolism in order to be able to survive in hypoxic conditions [8]. Rapidly proliferating cancer cells demonstrate a preferential bias toward aerobic glycolysis over oxidative phosphorylation for supporting growth and survival in hypoxic conditions. This metabolic reprogramming is referred to as the “Warburg effect”. Through this mechanism, tumor cells are able to produce large amounts of lactate while consuming very little oxygen. The dependency of cancer cell proliferation on accelerated glucose metabolism distinguishes them from their normal counterparts and could render them more vulnerable

to the disruption of glucose metabolism. Therefore, cancer cells could be selectively targeted by the disruption of intracellular glucose metabolism.

### **Hexokinase 2 in GBM metabolism**

Hexokinases (HKs) catalyze the first committed step in glucose metabolism, which is the ATP-dependent phosphorylation of glucose to glucose-6-phosphate (G6P), which ensures a sustained concentration gradient that promotes the entry of glucose into cells. This establishes the role of HK in determining the magnitude and direction of intracellular glucose flux. The HK family of enzymes is comprised of 4 isoforms (denoted as HK1, HK2, HK3, and HK4 [11]. Among these, HK1, and HK2, are associated with mitochondria and were also implicated in cell survival [12, 13]. While HK1 is present in most human adult tissues, HK2 is only expressed in embryonic tissues or a select group of adult tissues such as adipose and skeletal/cardiac muscles [14]. What distinguishes cancer cells from normal cells is their ability to express very high levels of HK2, which promotes the accelerated flux of glucose under hypoxic conditions [15, 16]. Over-expression of HK2 has been demonstrated in many cancer types and it has been associated with a poor survival [17].

Over-expression of HK2 has been documented in GBM cells as well [18, 19]. In addition to its role in promoting the influx of glucose, HK2 also inhibits apoptosis [20]. Previously, we have shown that while HK2 is significantly upregulated in GBM, HK1 was down-regulated [21]. Our group has also previously shown that a reduction of HK2 expression (but not HK1 or HK3) *in vitro* can inhibit aerobic glycolysis, increase normal oxidative respiration, and induce apoptosis (particularly under hypoxic conditions). We have also shown that the survival of mice injected with HK2 knockdown glioma cells is extended[19] and that HK2 plays a critical role in tumor cell survival at a very early stage [21].

Through microscopic analysis of tumor cells deficient of HK2, compared with controls, our group has also shown that HK2 has the ability to alter the tumor vasculature as well [21]. Our *in vitro* work has demonstrated a significant decrease in the density of neovasculature particularly away from the central necrotic core. *In vivo*, we demonstrated that mice bearing intracranial GBM xenografts of HK2- knock down tumors had a significantly decreased vascular perfusion/permeability compared to xenografts of control tumor, based on measurement of the  $K_{trans}$  value in dynamic contrast-enhanced MR imaging (Figure 1). Furthermore, we have also shown that the absence of HK2 confers sensitivity to chemo-radiation *in vivo* (Figure 2).

[figure not shown]

Figure 1. HK2 knock-down models mouse models of GBM demonstrate decreased microvascular density, diminished vascular permeability, and less dilated/ tortuous vessels

[figure not shown]

Figure 2. HK2 knock-down mouse models of GBM have a longer average survival compared to controls. This also increases the tumor cells' sensitivity to chemo-radiation (TMZ = radiation)

[figure not shown]
Therefore, it is clear that HK2 is a key driver of several oncogenic pathways in GBMs and is at least in part responsible for the tumor's increased proliferation and resistance to chemo-radiation. Currently, no direct inhibitor of HK2 has been tested in human patients with GBMs. Given the limited progress in the field of therapeutics for GBMs since the establishment of the Stupp protocol as the standard of care [22], there is a pressing need to expand the available treatment regimens for this population by

introducing new approaches or therapeutic agents. One possible means to expedite initiation of GBM clinical trials is to examine previously established drugs with a known track record of safety in humans, regardless of their intended use.

## 2.2 Previous Data

[figure not shown]
### Identification of the potentially anti-tumor effect of azoles in patients with GBM

Using a small drug screen targeting potential HK2 regulated gene expression networks we identified the azole class of antifungals as inhibitors of tumor metabolism by reducing proliferation, lactate production, glucose uptake in GBM cells but not primary normal human astrocytes or normal neural stem cells (Figure 3) [58].

### Ketoconazole and posaconazole enhance *in vitro* survival in part through down-regulation of HK2 activity

Upon identification of ketoconazole and posaconazole as potential inhibitors of HK2-regulated gene expression networks, we conducted dynamic metabolic flux analysis with C-labeling experiments followed by liquid chromatography-mass spectrometry (LC-MS) to assess the effect of the addition of ketoconazole or posaconazole, on glycolytic intermediates from GBM cell lines and Glioma stem cell cultures [58]. Through this approach, we demonstrated a reduction of various pro-anabolic glycolytic intermediates through the addition of these azoles (Figure 4A). This was shown to be at least in part due to the down-regulation of HK2 activity, and hence reduction of lactate production, by azoles (Figure 4 B, and C) Loss of HK2 in GBM cells dampened the effect of several azoles suggesting that the mechanism of action is mediated in part through HK2 (Figure 4D). The addition of ketoconazole or posaconazole (IC50 = 10  $\mu$ M) decreased the viability of several GBM cell lines (Figure 4E) and glioma stem cells (Figure 4F) but not normal human astrocytes (NHA).

[figure not shown]

Figure 4 D. Glioma cell line viability is decreased following treatment with Ketoconazole and Posaconazole. This effect on viability is decreased in the absence of HK2 (knock-down)

[figure not shown]

Figure 4E. Increasing concentrations of Ketoconazole and Posaconazole decrease the % viability of GBM cell lines but not normal human astrocytes (NHA).

[figure not shown]

Figure 4F. Increasing concentrations of ketoconazole and posaconazole decrease the viability of glioma stem cell lines but not normal stem cell lines (NSC).

#### Ketoconazole and posaconazole enhance *in vivo* survival in part through down-regulation of HK2 activity

The survival of U87 xenograft mice bearing glioblastoma tumors was extended through the administration of either ketoconazole or posaconazole (25mg/kg daily) (Figure 5A) [58]. Histologically, a decrease in mitotic activity was observed following the administration of these two agents in glioma cells (Figure 5 B and C). The reduction of HK2 activity following the administration of ketoconazole or posaconazole was demonstrated *in vivo* as well, with concordant reduction of lactate production as well (Figure 5 D and E).

Figure S1

[figure not shown]

Figure 5. Enhancement of xenograft survival following the administration of ketoconazole or posaconazole (A), along with decreased mitotic activity as demonstrated through Ki67 staining (B and C). This is mediated through reduction of HK activity (D) and lactate production (E).

## 2.3

### Study Rationale

Both ketoconazole and posaconazole are FDA-approved anti-fungal agents with a well-established side effect and safety profile. Ketoconazole and posaconazole have shown efficacy in reducing tumor cell proliferation in our *in vitro* studies. Furthermore, both have also shown efficacy, mediated at least in part through inhibition of HK2 activity, in our animal models with dosing concentration and schedules that are documented as safe in humans.[58] As a drug, posaconazole has a more predictable half-life than ketoconazole and has less off-target effects. Therefore, the proposed trial will focus on the role of posaconazole exclusively. As a first step, demonstration of adequate penetrance of study drug in brain and tumor tissue (pharmacokinetics) and biological effect (inhibition of glycolysis and subsequent tumor cell death) is necessary prior to large scale clinical studies. A total of 5 control participants will be included in this study as we specifically want to assess for pharmacodynamic differences too. The

addition of a control group to this study rather to both the studies (ketoconazole study is a separate protocol) is because we feel posaconazole may be a more promising drug for moving forward.

Plasma drug concentration measurements are an unreliable method to assess delivery of drugs across the blood-brain barrier. In contrast, intracerebral MDC monitoring allows for approximate measurements within extracellular fluid (ECF) sampling of the brain. MDC placement within the brain is not a novel technique and has been utilized routinely in the ICU setting to measure brain metabolism by sampling of ECF of traumatic brain injury patients [59-61].

MDC are now FDA-approved and are being placed routinely with intracranial pressure monitors. This method allows for continuous measurement of ECF within a tumor or normal tissue. The dialysis probe has a semipermeable membrane which is less than 1 mm in diameter into which two sections of microcatheter are fused. Previous studies have demonstrated the feasibility of keeping the catheters in place of critically injured patients for up to 2 weeks [62-64].

When placed at the time of surgical resection, the microcatheters are stereotactically implanted, placing the probe within the desired brain and/or tumor region. Externally, the catheter is connected to a syringe pump, which delivers a low flow rate ( $\mu\text{l}/\text{min}$ ) of continuous perfusion fluid (Lactated Ringers or artificial CSF) and dialysate is collected in a microvial from the outlet tube. This sterile, single use catheter is minimally invasive and developed to achieve optimal diffusing characteristics similar to passive diffusion of a capillary blood vessel. Just as in the function of brain capillary vessel, water, inorganic ions and small organic molecules freely diffuse across the membrane of the probe, whereas proteins and protein bound compounds are impermeable. Additionally, lipophilic compounds are poorly recovered. Therefore, assessment of pharmacokinetics of drug using MDC provides valuable insight relevant to its anti-neoplastic properties.

## 3.0 Inclusion and Exclusion Criteria

### 3.1 Inclusion Criteria

Patients eligible for enrollment in this study will be male and female adults with a presumed diagnosis of primary or recurrent HGG based on standard of care imaging (contrast-enhanced MRI) and clinical presentation and for whom surgical intervention has been selected as the most appropriate treatment option by the treating physician and patient.

1. Age  $\geq 18$  years
2. Evidence of primary or recurrent HGG that in the opinion of the treating team would require surgical resection
3. Adequate liver function defined as ALT, AST, ALP within 1.5x institutional upper limit of normal (for study drug arm only)
4. Ability to swallow medication (for study drug arm only)
5. Women of child-bearing potential and men must agree to use adequate contraception (hormonal or barrier method of birth control; abstinence) for the duration of study participation (for study drug arm only)
6. Ability to understand and willingness to sign a written informed consent document
7. Be able to comply with treatment plan, study procedures and follow-up examinations

### 3.2 Exclusion Criteria

1. Patients may not be receiving any other investigational agents while on study
2. Patients who have known allergy to posaconazole or other azoles (for study drug arm only)
3. Patients who have previously had a severe side effect, such as agranulocytosis and neutropenia, in conjunction with previous azole class drugs for a parasitic infection (for study drug arm only)
4. Patients with a history of acute or chronic hepatitis (for study drug arm only)

5. Patients with liver enzymes (ALT, AST, ALP) >1.5x above normal range for the laboratory performing the test (for study drug arm only)
6. Patients who are taking metronidazole and cannot be safely moved to a different antibiotic greater than 7 days prior to starting posaconazole therapy (for study drug arm only)
7. Patients who are taking any anti-convulsant medication that interferes with the cytochrome P450 pathway (e.g. phenytoin, phenobarbital, carbamazepine, etc.) and who cannot be switched to alternative medications such as Keppra (levetiracetam) (for study drug arm only)
8. Uncontrolled intercurrent illness such as chronic hepatitis, acute hepatitis, or psychiatric illness/social situation that would limit compliance with study requirements (for study drug arm only)
9. Patients with a history of Addison's disease or other forms of adrenal insufficiency (for study drug arm only)
10. Patient with little or no stomach acid production (achlorhydria) (for study drug arm only)
11. Pregnant and breastfeeding women
12. Patients with a history of any medical or psychiatric condition or laboratory abnormality that in the opinion of the investigator may increase the risks associated with the study participation or investigational product administration or may interfere with the interpretation of the results.
13. Patients who are not available for follow-up assessments or unable to comply with study requirements
14. Patients who are currently taking medications that induce the metabolism of posaconazole, such as isoniazid, nevirapine, rifamycins (such as rifabutin, rifampin), or St. John's wort and cannot be safely discontinued off of them for the duration of the trial (for study drug arm only).
15. Patients who are currently taking medications for which the metabolism may be affected by posaconazole, which include but are not limited to: benzodiazepines (such as alprazolam, midazolam, triazolam), domperidone, eletriptan, eplerenone, ergot drugs (such as ergotamine), nisoldipine, drugs used to treat erectile dysfunction-ED or pulmonary hypertension (such as sildenafil, tadalafil), some drugs used to treat seizures (such as carbamazepine, phenytoin), some statin drugs (such as atorvastatin, lovastatin, simvastatin) (for study drug arm only)
16. Patients who are non-English speakers
17. Patients who are not capable of understanding the consent form and would need a legally authorized representative

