### 7.4 Test Article(s) (Study Drug(s) and/or Study Device(s))

#### 7.4.1 Description

##### Classification:

Posaconazole is a second-generation triazole agent with a potent and broad antifungal activity. Posaconazole is available as concentrated solution to be diluted before intravenous administration, delayed-release tablet, or suspension for oral administration. Posaconazole is designated chemically as 4-[4-[4-[4-[(3R,5R)-5-(2,4-difluorophenyl)tetrahydro-5-(1H-1,2,4-triazol-1-ylmethyl)-3-furanyl]methoxy]phenyl]-1-piperazinyl]phenyl]-2-[(1S,2S)-1-ethyl-2-hydroxypropyl]-2,4-dihydro-3H-1,2,4-triazol-3-one with an empirical formula of C37H42F2N8O4 and a molecular weight of 700.8.

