### **10.0 Risks**

#### **Risk of drug**

While this drug has never been tested specifically in the HGG population, it is an FDA-approved drug. The potential side effects are:

Common side effects (occurring in at least 1 in 100 patients) are:

- Headache
- Dizziness
- numbness or tingling;
- sleepiness
- feeling or being sick
- loss of appetite
- stomach pain
- diarrhea
- upset stomach
- nausea
- vomiting
- flatulence (excessive gas in the digestive tract)
- dry mouth
- abnormal liver function tests
- rash
- weakness
- tiredness
- a decrease in white blood cells (that can increase the risk of infections)
- fever

- abnormal amounts of salts in the blood

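### Exclusion 3 counts a prior severe azole reaction only if the azole was given for a parasitic infection, so a reaction during antifungal use is left to investigator discretion

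*Combined protocol and SAP*

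**What the plan says.** Section 3.2, item 3, describes the patients to be kept out of the study drug arm as follows: "Patients who have previously had a severe side effect, such as agranulocytosis and neutropenia". The sentence then limits the circumstances: "in conjunction with previous azole class drugs for a parasitic infection". The event must therefore be severe, must have occurred on an azole, and that azole must have been prescribed for a parasite.

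The rest of the protocol treats the class as antifungal:

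- Section 2.2 (Previous Data): "we identified the azole class of antifungals as inhibitors of tumor metabolism".
- Section 2.3 (Study Rationale): "Both ketoconazole and posaconazole are FDA-approved anti-fungal agents".
- Section 7.4.1 (Description, Classification): "Posaconazole is a second-generation triazole agent with a potent and broad antifungal activity".

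Section 10.0 (Risk of drug) includes, among effects seen in at least 1 in 100 patients, "a decrease in white blood cells (that can increase the risk of infections".

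The neighbouring exclusion, item 2, reads "Patients who have known allergy to posaconazole or other azoles (for study drug arm only". It concerns allergy and does not mention blood toxicity.

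**The concern.** Item 3 names a type of toxicity and makes it a mandatory reason not to give posaconazole, but it then ties the exclusion to an indication that the protocol does not otherwise associate with this drug class. The prior exposure most obviously comparable to the study drug is an azole taken for a fungal infection, and a severe blood reaction during that exposure falls outside the item. Parasitic infection is mentioned nowhere else in the document, and nothing explains why the reason for the earlier prescription should matter.

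What is at stake is participant safety and consistent application of a named criterion in a drug arm of five. Two patients with the same reaction to the same azole would be handled differently according to what the azole had been prescribed for: one excluded by rule, the other considered case by case.

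**Working it through.** No figure in the plan depends on this criterion, so there is nothing to recompute. The check is to apply the criteria as written to three histories.

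| History of severe neutropenia or agranulocytosis | Meets item 3? | Other route to exclusion |
|---|---|---|
| On an azole given for a parasitic infection | Yes | Not needed |
| On an azole given for a fungal infection | No | Item 12 (discretionary); item 2 only if the event was also recorded as an allergy |
| On an azole given for another non-parasitic reason | No | As for a fungal infection |

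The other provisions were then read to see whether any of them closes the gap in the second and third rows.

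1. **Item 2 (section 3.2).** Known allergy to posaconazole or another azole. Marrow toxicity without an allergic label is not covered.
2. **Items 4 and 5 (section 3.2).** History of hepatitis and current liver enzymes. Neither concerns blood counts.
3. **Inclusion criteria (section 3.1).** The only laboratory limit is on liver function. No neutrophil, white-cell or platelet limit appears in 3.1 or 3.2.
4. **Screening (section 7.2.1).** A CBC is obtained at Visit 1 or taken from the record if done within 31 days of consent. It shows the present count and not a past reaction, and no eligibility threshold is attached to it.
5. **Contraindications (section 7.4.6.5).** The list is stated not to be exhaustive. It deals with hypersensitivity and co-administered drugs, and does not mention earlier blood toxicity.
6. **Item 12 (section 3.2).** Any medical history or laboratory abnormality that the investigator thinks may raise the risk of receiving the product. A past azole-related agranulocytosis fits this well, but the item does not name it and its use is a matter of opinion.

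The gap in item 3 is therefore real, and the only provision that readily reaches these patients is discretionary.

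**The case against.** The strongest reply is that item 12 already deals with such a patient. Its terms fit closely, medical history is taken at Visit 1, the trial is single-center, the principal investigator identifies potential subjects, and only five patients are to be treated. The usual worry about discretionary criteria, that sites apply them differently, has little force here. This stands as a limit on the consequence: the protocol never requires such a patient to be enrolled. It does not repair item 3. The protocol chose to name this toxicity as a fixed exclusion, and a discretionary item does not do the same work.

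It is also fair to say that intent is inferred. The documents do not give the reason for the qualifier, so a deliberate restriction cannot be ruled out. They give no rate at which blood toxicity recurs on a second azole. Section 10.0 lists the white-cell fall without a grade, and agranulocytosis does not appear in its drug risk lists.

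Some stronger readings are tempting but are not supported:

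- A reader might infer that item 3 works in reverse and excludes the wrong patients. The qualifier restricts the indication and not the drug, so an antifungal azole given for a parasitic infection is still covered. The item is too narrow; it is not backwards.
- A reader might point to the stopping rule in section 18.7, since one drug-attributed grade 4 event would be 1/5 = 20% of the arm and one of the two events that halt accrual. That is true of such an event from any cause and does not measure this gap.
- A reader might link the gap to the 1% catheter infection risk in section 10.0. The documents do not connect that figure to neutropenia or to this criterion.
- A reader might add that no CBC is scheduled after Visit 1. That is a separate monitoring matter, which rewording item 3 would not change.

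**Conclusion.** The point holds as a wording defect in a safety exclusion. Read literally, item 3 does not reach a severe reaction, such as agranulocytosis or neutropenia, to an azole given for a fungal or other non-parasitic indication, although the protocol presents the class as antifungal and lists a white-cell decrease as a common effect. Only the discretionary item 12 would ordinarily keep such a patient out.

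The size is small. Few patients are likely to have this history, possibly none among the five treated, and the documents give no figure from which a frequency or a recurrence risk could be derived. No endpoint, estimate, success criterion or sample size is affected. The conclusion rests on a literal reading of item 3 and on the assumption that the qualifier has no undocumented rationale. The correction is worth making because it concerns participant protection and costs almost nothing.

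**What to change.** Reconcile item 3 of section 3.2 with the drug class described in sections 2.2, 2.3 and 7.4.1 and with the toxicity listed in section 10.0, so that the exclusion does not turn on why the earlier azole was prescribed. The evident edit is to delete the four words that specify the indication and leave the event types and the restriction to the study drug arm as they are. If the sponsor and investigator intend the restriction, the protocol should state the reason next to the item. The clinical scope of the criterion is theirs to decide.

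The cost is a short protocol amendment, with no added test, visit or sample. The effect on recruitment should be negligible: the item applies to the drug arm only, and section 7.2 already routes patients who cannot take posaconazole first to the ketoconazole study and then to possible candidacy for the control arm while places remain.
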